## **6. STATISTICAL METHODS AND DETERMINATION OF SAMPLE SIZE**

### **6.1 Statistical and Analytical Plans**

The aim of this long-term extension study is primarily the assessment of safety and tolerability, so no single primary variable has been identified. Patient numbers will be determined by those completing the PATENT-1 study and willing to enter the PATENT-2 study. As the extension is of an open label design with no comparator group, all statistical analyses will be descriptive. The summary tables will be presented for the overall group of patients, and also split by previous treatment groups in PATENT-1. Baseline will be week 0 in PATENT-1 (changed with amendment 11).

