#### **10.4 6 Min Walking Distance (6MWD) Test**

The 6MWD Test must be performed in accordance with the American Thoracic Society Guideline ([American Thoracic Society. ATS Statement: Guidelines for Six-Minute Walk Test. American Journal of Respiratory and Critical Care Medicine 2002; Vol 166. pp 111-117](#))

According to the guideline, the 6MWD Test should be carried out indoors, along a long, flat, straight, enclosed corridor with hard surface that is seldom traveled. The walking course should be preferably 30 m in length but not less than 25 meters (longer walking courses should be shortened to 30 m). The length of the corridor and turnaround points should be marked.

Patients will be instructed to walk alone, not run, from one end to the other end of the walking course, at their own pace, while attempting to cover as much ground as possible in 6 min.

During the walk, patients are allowed to stop, lean against the wall and rest, but should resume walking as soon as they feel able to do so.

A “warm-up” period before the test should not be performed. The patients should sit at rest in a chair, located near the starting position, for at least 10 minutes before the test starts.

Investigators should not walk with the patients. Moreover, only standardized phrases for encouragement must be used during the test. To allow reproducibility, standardized phrases should be used every minute according to the following pattern:

- After the first minute, tell the patient the following (in even tones): “You are doing well. You have 5 minutes to go.”
- When the timer shows 4 minutes remaining, tell the patient the following: “Keep up the good work. You have 4 minutes to go.”
- When the timer shows 3 minutes remaining, tell the patient the following: “You are doing well. You are halfway done.”
- When the timer shows 2 minutes remaining, tell the patient the following: “Keep up the good work. You have only 2 minutes left.”
- When the timer shows only 1 minute remaining, tell the patient: “You are doing well. You have only 1 minute to go.”

To reduce the variability of the 6MWD Tests, it is of utmost importance that the eligibility-test, the baseline-test and all following tests are performed under the same conditions (truncated with amendment 11):

- Patients, who used walking aids already at the eligibility-test and the baseline-test (eg cane, walker), need to use the same walking aids at every subsequent 6MWD Test.

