6.2 Efficacy

Efficacy variables are:

- 6 minute walking distance from the 6MWT
- PVR (no RHC required at any time during study, PVR only measured if RHC performed as part of regular diagnostic work up)
- NT pro-BNP
- WHO functional class
- Time to clinical worsening
- Borg CR 10 Scale[®]
- EQ-5D questionnaire
- LPH questionnaire

In the efficacy analyses, countries and centres will be clustered by geographic region, consistent with the pooling in study 12934.

All analyses will be descriptive. For non-categorical data, absolute values and changes from baseline will be summarized. Baseline will be week 0 of study 12934.

It is envisaged that WHO functional class will either remain the same, improve by one or two categories, or deteriorate by one category in most cases. A change score (end of study minus baseline) will be calculated, which could go from -3 (class IV at baseline and class I at end of study) to +4 (class I at baseline, death at end of study), but in practice for those patients still alive at the end of the study it will most likely range from -2 to +1

Time to clinical worsening is made up of several components:

- 1) all-cause mortality
 - 2) heart/lung transplantation
 - 3) Atrial septostomy (AS)
 - 4) hospitalization due to persistent worsening of pulmonary hypertension
 - 5) start of new PH-specific treatment
 - 6) persistent decrease in 6MWD
 - 7) persistent worsening of functional class
- as defined in the protocol section 4.6.4.

The occurrence of the event of clinical worsening during the long-term extension will be summarized using categorical methods, but as an additional summary, the time to event will also be described. In determining whether an event is considered to be an event of clinical worsening the same rules as in study 12934 will be applied.

Change in the Borg CR 10 Scale[®] will be summarized using frequency counts.

The exploratory efficacy variables described in the Supplementary SAP of study 12934 will be summarized descriptively. This includes the subscales of the EQ5D and LPH and the additional haemodynamic variables. Also the sensitivity analysis of clinical worsening and the categorical analyses described in the Supplementary SAP of study 12934 will be performed.

The primary and secondary efficacy variables, except PVR, will be summarized descriptively for the following subgroups:

- therapy-naïve
- pre-treated
- pre-treated with Endothelin Receptor Antagonist
- pre-treated with Prostacyclin Analogue
- region

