- idiopathic/familial PAH
- connective tissue disease
- associated (other forms) PAH
- WHO FC I/II at baseline
- WHO FC III/IV at baseline
- therapy-naïve and WHO FC I/II at baseline
- therapy-naïve and WHO FC III/IV at baseline
- pre-treated and WHO FC I/II at baseline
- pre-treated and WHO FC III/IV at baseline
- < 320m 6MWD at baseline
- ≥ 320m 6MWD at baseline
- < 380m 6MWD at baseline
- ≥ 380m 6MWD at baseline
- males
- females
- age < 65 years

- age \geq 65 years
- race.

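### 6MWD change from week 0 is tabulated in subgroups cut on that same week-0 walk, so regression to the mean exaggerates the difference in change between low and high walkers (minor; cheap to improve)

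*SAP*

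**What the plan says.** SAP 6.2 sets the measure and the reference point together: "For non-categorical data, absolute values and changes from baseline will be summarized. Baseline will be week 0 of study 12934". Protocol 6.1 fixes the same baseline.

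SAP 6.2 then states: "The primary and secondary efficacy variables, except PVR, will be summarized descriptively for the following subgroups". 6MWD is among the listed efficacy variables and only PVR is left out, so walking distance is itself summarised in subgroups defined by walking distance. Four of these are "< 320m 6MWD at baseline", its complement at or above 320 m, and the matching pair at 380 m.

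On the absence of a control, Protocol 6.1 says: "As the extension is of an open label design with no comparator group, all statistical analyses will be descriptive". SAP 6 splits tables by former PATENT-1 treatment, but former placebo patients take riociguat in the extension, so that split is not a concurrent control.

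A second pre-treatment walk exists. Protocol 10.4 says that "it is of utmost importance that the eligibility-test, the baseline-test and all following tests are performed under the same conditions", which names eligibility and baseline as separate tests. Neither document uses the eligibility walk to form subgroups, plans a baseline-adjusted summary, or mentions regression to the mean.

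**The concern.** A single walk is the patient's usual distance plus test error. Patients fall below a cut partly because that walk was low for them, and above it partly because it was high for them. On any later walk the error is drawn afresh, so the low group moves up and the high group moves down without any drug effect. In a randomised comparison both arms carry the same shift and it cancels. Here it stays in the printed subgroup mean, and more patients do not reduce it.

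What is at stake is the comparison of level. A reader who sets the low-walk row beside the high-walk row would conclude that patients with shorter baseline walks gain more, when some or all of that contrast may be test noise. No formal test is planned, so these means are what readers will interpret.

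**Working it through.** The plan states no figure on this point and the sample size section is marked as not applicable, so there is nothing to reproduce. The check is whether the artefact exists, what it touches, and how large it could be.

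**Inputs.** From the documents: the cuts c = 320 m and 380 m, change taken from the same week-0 walk, and no comparator. Assumed, because the documents do not give them: mean μ = 360 m, between-patient SD σ_b = 60-70 m, single-test SD σ_e = 20, 30 or 40 m, normal distributions, independent test errors, and no true change.

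**Formulas.** Let σ² = σ_b² + σ_e², 1 − r = σ_e²/σ² (r is the test-retest correlation) and a = (c − μ)/σ, with φ and Φ the standard normal density and distribution function.

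- Mean change below the cut = +(1 − r)·σ·φ(a)/Φ(a)
- Mean change at or above the cut = −(1 − r)·σ·φ(a)/(1 − Φ(a))

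**One case in full** (σ_b = 60, σ_e = 20, c = 320): σ = √(3600 + 400) = 63.25; 1 − r = 400/4000 = 0.10; a = −40/63.25 = −0.632; φ = 0.3266; Φ = 0.2635.

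- Low: 0.10 × 63.25 × 0.3266/0.2635 = +7.8 m
- High: −0.10 × 63.25 × 0.3266/0.7365 = −2.8 m
- Gap: 10.6 m

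**All cases** (ranges over σ_b = 60-70 m; changes and gaps in metres):

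| σ_e | r | 320 m: low | 320 m: high | 320 m: gap | 380 m: low | 380 m: high | 380 m: gap |
|---|---|---|---|---|---|---|---|
| 20 | 0.90-0.93 | +6.5 to +7.8 | −2.7 to −2.8 | 9.1-10.6 | +3.5 to +3.8 | −5.4 to −6.4 | 8.9-10.2 |
| 30 | 0.80-0.85 | +13.7 to +16.3 | −5.9 to −6.2 | 19.6-22.4 | +7.5 to +8.3 | −11.5 to −13.4 | 19.0-21.7 |
| 40 | 0.69-0.75 | +22.6 to +26.2 | −10.1 to −10.7 | 32.7-36.9 | +12.8 to +14.0 | −19.1 to −21.8 | 31.9-35.8 |

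Simulation with 2,000,000 patients agrees. Over a different assumed grid (μ 340-380 m, total SD 60-100 m, r 0.80-0.95) the gap runs from 4.9 to 33.5 m at 320 m and from 4.8 to 32.6 m at 380 m. The sign never changes.

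**What is not touched.**

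- *Whole-group change.* Weighting the two subgroups by their sizes gives zero. In the worked case, 0.2635 × 7.8 ≈ 2.1 and 0.7365 × 2.8 ≈ 2.1, with opposite signs.
- *Course within the extension.* With stable true values, two later walks have the same covariance with the week-0 walk, so the expected change between them is zero in every subgroup. Simulation gave values within 0.1 m of zero. The offset is complete by the first walk after week 0, which falls inside PATENT-1.

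**With a true gain.** Take total SD 70 m, r = 0.90 and a uniform true gain of 30 m. At 320 m the noise terms are +8.4 and −3.3 m, so the table would show 30 + 8.4 = 38.4 m against 30 − 3.3 = 26.7 m. Both subgroups improve, and the difference of about 12 m is false.

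**Grouping on the eligibility walk.** Let k be the correlation between eligibility and baseline test errors. Given the eligibility walk x, the expected change is −k(1 − r)(x − μ), so the gap is k times the gap in the table. It is zero at k = 0. At σ_b = 65 and σ_e = 30 the 320 m gap of 20.9 m falls to 0.3 × 20.9 = 6.3 m or 0.5 × 20.9 = 10.5 m.

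**The case against.** The strongest reply is about consequence. The trial's purpose is safety and tolerability, there is no primary variable, every analysis is descriptive, and no decision rests on these four rows of a long subgroup list. Summarising change by baseline severity is conventional. This stands, and it sets the severity at minor.

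A reader might go further and infer that the tables would make benefit look better maintained in low walkers and lost over time in high walkers. The plan does not support that. The offset is already present when patients enter the extension and stays roughly constant, so it cannot create a trend. SAP 6.2 also reports absolute values, from which the visit-to-visit course can be read without this artefact. A reader might likewise expect the high subgroup to decline. That follows only if there is no true gain; otherwise it may show just a smaller gain.

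The size is also open to challenge. No mean, SD or retest error is in the documents, and the top of the range needs a test SD of 40 m, which implies r of only 0.69-0.75. Protocol 10.4 works to limit noise through a standard course, rest period and phrases, and a familiarisation walk for patients new to the test. This argues for the lower part of the range but does not remove the bias, because any r below 1 gives the same direction.

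Finally, the eligibility-walk grouping removes the bias fully only if the two test errors are independent. The documents do not give the interval between those walks, and errors on nearby days may be correlated. This stands too, and is why that grouping is proposed as an added table rather than a replacement.

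**Conclusion.** The point holds in a limited form. Using the week-0 walk both to classify patients and as the reference for change, with no comparator, biases the subgroup means in a known direction and exaggerates the difference in level of change between low and high walkers. The direction needs only imperfect test-retest agreement. The size rests wholly on assumption: about 9-37 m under the values used here, and about 9-11 m if the single-test SD is 20 m.

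The documents do not support reading this as a distortion of the whole-group change, of maintenance of effect during the extension, or as a forecast that high walkers will be seen to decline. The imputation of 0 m in SAP 4.3 can also move subgroup means, but that is a separate matter. This is a minor point and a cheap improvement.

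**What to change.** In SAP 6.2, add a summary of 6MWD change from week 0 in which the 320 m and 380 m subgroups are formed from the PATENT-1 eligibility 6MWD, and state that this table is the one to use when comparing change between low and high walkers. Keep the week-0 split for comparability with study 12934, with a footnote that its change from baseline includes regression to the mean.

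The cost is one extra table and one merge with PATENT-1 data. This assumes that the eligibility distance was recorded there and can be retrieved; the protocol names the test but does not describe how it was recorded. Some patients near the cuts will sit in a different subgroup in the two tables. If eligibility and baseline errors are correlated the bias is reduced rather than removed: about half the gap remains at an error correlation of 0.5.

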6.3 Pharmacokinetics/pharmacodynamics

BAY 63-2521 and BAY 60-4552 trough concentrations will be summarized per visit, separated according to actual dose. The analyses will be focused on descriptive statistics. The following statistics will be calculated for each of the sampling points: arithmetic mean, standard deviation and coefficient of variation (CV), geometric mean, geometric standard deviation (re-transformed standard deviation of the logarithms), and CV, minimum, median, maximum value and the number of measurements. Means at any time will only be calculated if at least 2/3 of the individual data were measured and were above the limit of quantification (LOQ). For the calculation of the mean value a data point below LOQ will be substituted by one half of the limit. In tables showing mean values, this means will be marked. Tables will be split by scheduled/ unscheduled visits.

Boxplots of plasma concentrations of BAY 63-2521 and BAY 60-4552 at each visit will be given for scheduled extension visits and the last visit of the main study 12934. Separate plots will be given for each of the former treatment groups (“Riociguat Individual Dose Titration”, “Riociguat 1.5 mg Dose”, “Placebo”). The plots will be restricted to patients that, while receiving riociguat, have been uptitrated at all planned times and have not been down-titrated until visit 5 of the extension study.

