**Patients from the PATENT-1 Placebo Arm:**

For patients from the PATENT-1 Placebo Arm the starting dose will be 1 mg BAY 63-2521 tid. The individual BAY 63-2521 dose will be titrated every 2 weeks according to the peripheral SBP measured at trough before intake of the next morning dose. At the end of the Titration Phase (Visit 5) patients will have reached BAY 63-2521 doses between 0.5 mg tid and 2.5 mg tid.

Titration phase the same titration rules as for the PATENT-1 placebo patients, the individual dose cannot be increased above the dose received at last day of PATENT-1. If the investigator requests a dose increase above that level via the IVR-System, the patient will undergo a sham titration. Nevertheless, in case that the investigator requests a dose decrease (eg for safety reason), dose modifications are possible, but without a subsequent re-increase before Visit 5.

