## **4.5 Treatments**

### **4.5.1 Treatments to be administered**

Test-Drug:	BAY 63-2521
Dosage:	1.0 - 2.5 mg (Individual Dose Titration) a
Route of administration:	oral
Time and frequency of administration:	tid b

aIn case of side effects (eg symptomatic hypotension) doses of 0.5 mg tid are allowed

bThe respective single daily doses should be taken 6-8 hours apart.

(For the individual dose titration refer to Section 4.1.)

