#### 4.6.3 Assessment Periods

##### Visit 1 at Day 0

Patients who finalized at Visit 6 the PATENT-1 trial and underwent invasive hemodynamic measurements may remain in the clinic until the next day (optional hospital stay).

At the day after finalization of PATENT-1 trial (= Visit 1 of PATENT -2), patients who fulfill the in/exclusion criteria and signed the informed consent form will be included into PATENT -2.

**Please Note:** it is not permitted to include a patient into the extension study on the same day of V6 of PATENT -1 (applies even if Visit 6 investigations were performed at two consecutive days).

On Visit 1 prior to first administration of PATENT-2 study medication, blood pressure and heart rate will be measured.

Subsequently, the patients will be allocated via the IVR-System to their individual BAY 63-2521 starting dose. In this context, the IVR-System will consider the patient's treatment arm allocation from the PATENT-1 trial (for further details refer to Section 4.1).

Two to three hours after the first intake of study medication, blood pressure and heart rate measurement will be repeated (for further details about the order of the procedures and the temporal relationship refer to Section 10.1).

Between six to eight hours after first study medication intake, the patients should take the second dose of study medication (second measurement cycle). One to zero hours before intake of second dose of study medication, blood pressure and heart rate will be measured, pharmacokinetic blood samples will be collected and a 12-lead electrocardiogram will be recorded. 2-3 hours after intake of second dose of study medication the blood pressure and heart rate should be measured (for further details about the order of the procedures and the temporal relationship refer to Section 10.1).

In addition to the measurements related to the measurement cycles, Adverse Events will be questioned and documented. Adverse events that occur before intake of first dose of PATENT-2 medication will be allocated to PATENT-1.

The study medication should be taken six to eight hours apart. If during the profile visit the systolic blood pressure falls below 90 mmHg with clinical symptoms of hypotension such as dizziness or presyncope, the study medication should be reduced by 0.5 mg tid or if deemed necessary interrupted (see section 4.1).

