#### **4.6.5 Drug Concentration Measurements**

For investigation of drug exposure and potential relationships to drug effects, plasma concentrations of BAY 63-2521 (and its main metabolite BAY 60-4552)

will be determined at the times given in the Trial Flow Chart (see Section 10.1) and in the Appendix 10.2 using a sparse sampling approach in all participating patients.

Frequency: Visit 1 and Visit 5

BAY 63-2521 and metabolite M-1 (BAY 60-4552) concentrations in plasma will be measured by a validated HPLC-MS/MS method. Quality control (QC) and calibration samples will be analyzed concurrently with study samples. The results of QC samples will be reported together with concentrations in unknown samples in the MRR of this study. Drug concentrations are calculated from the chromatographic raw data in accordance with current Bayer guidelines (see Section 9). The data are evaluated using CCW software in its most recently released version.

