### **Visit 1**

Point in time: -01-00 hours before administration of the second dose of BAY 63-2521 (Day 1)

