### **V 5**

At this study visit the patients should present themselves to the hospital without taking the morning dose of BAY 63-2521. During the visit the pharmacokinetic sample should always be taken at trough before administration of the morning dose of study medication.

Point in time: -01-00 hours before administration of BAY 63-2521 morning dose

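### SAP 6.3 calls the former placebo patients' Visit 1 sample a trough; it is a single-dose level, and in the Visit 1, 1.0 mg cell it is pooled with repeated-dose levels

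*SAP*

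**What the plan says.** SAP 6.3 (Pharmacokinetics/pharmacodynamics) plans that "BAY 63-2521 and BAY 60-4552 trough concentrations will be summarized per visit, separated according to actual dose". The sentence does not mention former treatment group or first-dose status. The boxplots in the same section are drawn separately for the three former PATENT-1 groups.

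Protocol 4.6.5 schedules the samples: "Frequency: Visit 1 and Visit 5". Protocol 10.2 gives the times. At Visit 1 the sample is due -1 to 0 "hours before administration of the second dose of BAY 63-2521", and Protocol 4.6.3 places that second dose six to eight hours after the first. For the other visit, 10.2 says: "During the visit the pharmacokinetic sample should always be taken at trough before administration of the morning dose of study medication". Section 10.2 uses the word trough for Visit 5 only.

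On dosing, Protocol 4.1 says: "For patients from the PATENT-1 Placebo Arm the starting dose will be 1 mg BAY 63-2521 tid". Under the same section, former riociguat patients enter on their last PATENT-1 dose. On spacing, Protocol 4.5.1 says: "The respective single daily doses should be taken 6-8 hours apart".

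SAP section 6 sets a default for descriptive analyses unless something else is specified: all subjects, riociguat individual titration, and placebo-riociguat. The former 1.5 mg group is not in that list.

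**The concern.** A trough in a three-times-daily regimen carries what is left of earlier doses. A former placebo patient at Visit 1 has no earlier doses, so the value reflects one dose alone. A former riociguat patient sampled at the same moment has weeks of dosing behind the value. A table split only by visit and actual dose cannot tell the two apart when both are on 1.0 mg.

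A reader who takes the Visit 1, 1.0 mg summary as trough exposure at 1.0 mg three times daily would then be reading too low a figure. In former placebo patients, a reader comparing Visit 1 with Visit 5 would see a difference that comes partly from accumulation and partly from a different time after dose. Protocol 4.6.5 says the sampling is meant to describe exposure and its possible relation to effects, and Protocol 4.5.8 adds that concentrations inform compliance. Both uses depend on knowing what kind of level is tabulated.

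**Working it through.** The plan states no PK figure on this point, so there is nothing to reproduce. The check has three steps.

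**1. Sampling windows, from the protocol**

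- Visit 1: second dose 6-8 h after the first, sample 0-1 h before it. Earliest 6 - 1 = 5 h, latest 8 - 0 = 8 h after the first extension dose.
- Visit 5: with doses 6-8 h apart, the overnight gap is 24 - 2 × 8 = 8 h to 24 - 2 × 6 = 12 h. The sample is 0-1 h before the morning dose, so 8 - 1 = 7 h to 12 h after the evening dose.

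**2. Which cells can mix**

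All former placebo patients are on 1.0 mg at Visit 1, so first-dose values occur only in the Visit 1, 1.0 mg cell. The Visit 1 cells at 0.5, 1.5, 2.0 and 2.5 mg hold repeated-dose values only, and so does every Visit 5 cell. The other members of the mixed cell are former riociguat patients who ended PATENT-1 on 1.0 mg. They can come from either active arm; SAP section 3 provides for capped-dose patients whose last dose was 1.0 mg.

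Under the section 6 default, the placebo-riociguat column would be purely first-dose at Visit 1. The all-subjects row would still mix, and the former 1.5 mg patients would appear only there.

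**3. Illustrative size**

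Assumptions, none from the documents: parent drug, one compartment, absorption complete, equal doses, level proportional to exp(-kt) with k = ln 2 / half-life, half-lives of 4, 7 and 12 h, and no break in dosing for former riociguat patients. With doses at 0, 7 and 14 h:

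- First dose at Visit 1: F = e^(-7k)
- Repeated dosing at Visit 1: S1 = (e^(-7k) + e^(-17k) + e^(-24k)) / (1 - e^(-24k))
- Repeated dosing at Visit 5: S5 = (e^(-10k) + e^(-17k) + e^(-24k)) / (1 - e^(-24k))

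For a 4 h half-life: F = 0.297; S1 = (0.297 + 0.053 + 0.016) / 0.984 = 0.371; S5 = (0.177 + 0.053 + 0.016) / 0.984 = 0.249.

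| Half-life (assumed) | F | S1 | S5 | S1/F | S5/F | S5/S1 |
|---|---|---|---|---|---|---|
| 4 h | 0.297 | 0.371 | 0.249 | 1.25 | 0.84 | 0.67 |
| 7 h | 0.500 | 0.858 | 0.717 | 1.72 | 1.43 | 0.83 |
| 12 h | 0.667 | 1.723 | 1.581 | 2.58 | 2.37 | 0.92 |

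Taking all samples up to 1 h earlier multiplies F, S1 and S5 by the same factor and leaves the ratios unchanged. Changing the spacing to 6 h or 8 h moves S5/F to between 0.53 (4 h half-life, 6 h spacing) and 2.70 (12 h half-life, 8 h spacing).

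If a share w of the mixed cell is former placebo, its mean relative to the repeated-dose level is (1 - w) + w/(S1/F). Group counts are not given. For an assumed w of 0.5 to 0.9 at 7 h spacing, this is 0.90-0.82 (4 h), 0.79-0.62 (7 h) and 0.69-0.45 (12 h).

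**The case against.** The strongest reply is that the plan already does most of this. The section 6 default covers all descriptive analyses, and separating by dose need not cancel it; if it applies, former placebo patients have their own column. The boxplots are split by former group and refer to plasma concentrations, not troughs. They are also restricted to patients up-titrated at every planned time and not down-titrated, so a former placebo patient in them goes from 1.0 mg to 2.5 mg (1.0, 1.5, 2.0, 2.5). That plot cannot be taken for a same-dose comparison. No change from Visit 1 to Visit 5, accumulation ratio or test is planned from the tables, and table layouts sit in a separate specification that is not available here.

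Much of that stands. A reader might infer that first-dose and steady-state levels are mixed throughout the PK tables, or that the two visits are pooled. The documents do not support this: tables are per visit, and mixing is possible in one cell only. A reader might also infer that exposure would appear to rise from Visit 1 to Visit 5. That is not supported either, since the illustrative ratio runs from below 1 to above 2. For former riociguat patients both visits follow repeated dosing, and only the daytime versus overnight interval differs.

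What the reply does not remove: SAP 6.3 specifies its own split, and nothing says whether the default still applies. Even if it does, the all-subjects row mixes and the former 1.5 mg group has no column. The placebo-riociguat column would still present a first-dose value as a trough.

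**Conclusion.** The point holds as a limited correction to a descriptive analysis. That the former placebo patients' Visit 1 value is a single-dose level, that SAP 6.3 labels it a trough, and that the Visit 1, 1.0 mg cell can combine it with repeated-dose values all follow from the text without any pharmacokinetic assumption. So does the lack of like-for-like timing between Visit 1 and Visit 5 in these patients (5-8 h after a first dose against 7-12 h after an evening dose).

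The size does not follow from the text. It rests on assumed half-lives and a simple model for the parent drug; the metabolite BAY 60-4552, which shares the tables, was not modelled. Nor can the share of the mixed cell that is former placebo be established, so the distortion could be small. Efficacy and safety summaries are not affected.

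**What to change.** In SAP 6.3:

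- Tabulate Visit 1 concentrations by all three former PATENT-1 groups (individual titration, 1.5 mg, placebo), as the boxplots already are, and say how this relates to the section 6 default.
- Label the former placebo values at Visit 1 as *first dose, before second dose*, and do not pool them with repeated-dose values in the 1.0 mg all-subjects summary.
- Report actual time since last dose with each summary.
- Define actual dose as the dose taken before the sample. At Visit 5 the sample precedes that visit's dose decision (Protocol 4.6.3), so the term is otherwise ambiguous.

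The cost is a few lines of SAP text and one further table split. The data exist: Protocol 10.1 has dosing and sampling times documented in the case report form, and Protocol 4.6.3 has the times of the last three doses before Visit 5 recorded.
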